6.4 Reaction Management

It is possible that SRs may experience distress when watching these videos. However, these videos will be pre-screened by the study team for quality control. SRs may experience distress when filling in questionnaires and taking part in qualitative interviews. However, these questionnaires contain minimally (if at all) distressing topics, and the topic of qualitative interviews will be entirely on the intervention, so this is an unlikely risk. Additionally, to mitigate this concern, they will be informed that they can skip any questions for any reason, and there will be the option to "prefer not to answer" on every questionnaire question. If participants experience severe emotional distress as a result of their participation in this research, the study team will refer them to mental health resources where appropriate.

6.5 Withdrawal Procedures

Participants may withdraw from the study at any time. If they request to have their data not used in the analysis, their data will be destroyed. If not, their data will be kept in de-identified form. SPs may withdraw their consent to use their videos at any time, and their videos will be deleted and no longer used as part of the intervention.

6.6 Locations/Facilities

The entire study will be conducted via Zoom, Quatrics and REDCap.

7 Statistical Design

7.1 Sample Size Considerations

Sample size for the intervention was inferred from other pilot studies of behavioral interventions. Sample size for qualitative interviews was derived from prior qualitative work conducted by members of the research team.

Protocol Number 2000035434

7/23/24 v10

7.2 Planned Analyses

Intervention: Standard statistical analyses will be used to determine preliminary efficacy (e.g., random effects regression models) of continuously measured primary (percentage of days abstinent) and secondary (percentage of heavy drinking days) outcomes, measured at three time points (prior to intervention, post-intervention, and one-month post-intervention).

Video ratings done by SRs will be correlated with features of the SP videos to determine what components of the videos are associated with the video having motivational and supportive properties. We will only analyze videos in which SPs consent to their videos being used "in research publications where the content of their videos and information is analyzed".

Some examples of video features include the content of the video (e.g., higher proportion of sentences conveying esteem social support), audio (e.g., higher voice pitch variability), and visual (e.g., percent time making eye contact with the camera). To quantify content, videos will be manually transcribed by the PI to extract textual data. This transcript will be de-identified by removing all names of people and recovery organizations. Some examples of types of qualitative analyses that will be performed include content analysis on the textual data using the Social Support Behavior Code (Cutrona & Suhr, 1992) as a coding scheme, where sentences will be labeled as information, network, esteem, and/or emotional support. A text analysis application called Linguistic Inquiry and Word Count (LIWC, Boyd et al., 2022) will also be utilized to characterize the text based on various psychosocial constructs. For example, the word "cried" is classified in the affect category amongst others. Use of self-disclosure or stigmatizing language will be coded in binary (absent/present).

Audio data will be extracted from videos using software such as Adobe Premiere Pro. Quantitative analyses on audio data include using speech analysis software like Praat (Boersma, 2001) to extract audio features such as speech rate (a measure of how quickly the person in the video speaks), variability in waveform amplitude (as a measure of variability of how loudly one speaks) and variability in fundamental frequency (as a measure of how monotonous or prosidic the voice is). Examples of analyses of visual data include manual coding of percent time the person in the video spends looking at the camera versus visibly reading off a script, spontaneous blink rate (as a proxy of dopaminergic tone and arousal), and use of software such as OpenFace (Baltrusaitis et al., 2016) to quantify facial action units such as frequency of raising eyebrows and smiling. We may also use other software to quantify the colorfulness of the video and may qualitatively describe the background location where the video is set (e.g., fake zoom background, person's living room).

For most of the analyses described, at least two members of the study team will serve as coders/raters, and inter-rater reliability will be determined to ensure consistency. After these analyses have been completed, descriptive statistics will be used to summarize the characteristics. Statistical analyses will also be used to determine whether video characteristics differ as a function of demographics of the people in the videos. (For example, are men more likely to have monotonous speech patterns than women?) Then, after the rating data from are collected, correlational analyses will be performed to identify associations between content/audio/visual video variables and rating scores. Qualitative analyses of comments left by SRs about videos may also be incorporated to inform what SRs like and dislike about the videos.

QI: All participants' data will be analyzed unless otherwise specified by the participant. Data collected from QIs of support-providers will be analyzed separately from QIs of support-receivers.

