3.3 Objectives

The primary objectives of this study are to determine whether LDART is feasible, acceptable, and efficacious in reducing alcohol use and increasing engagement with recovery support services in adults who engage in hazardous alcohol use.

The secondary objectives are to determine whether video collection is feasible, to identify ways to improve this intervention, and to identify components of the videos recorded by SPs that were well-received by SRs.

4 Study Design

[figure not shown]

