4.2.2 Secondary and Exploratory Outcome Variables/Endpoints (if applicable)

Qualitative data with SPs and SRs after the intervention will identify barriers and facilitators to this intervention, and how to optimize it. Content analysis of SP videos will identify themes that they believe to be important in communicating to people in recovery. We will characterize the video content created by support-providers (e.g., speech rate, eye contact with camera) and correlate them with support-receivers' ratings of the content, to identify which characteristics are well-received by support-receivers, to guide future content creation.

5 Study Participants

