6.1 Study Procedures

SP protocol: After consent is complete, they will click on a Qualtrics link (*SP video-recording link*) to record two short videos to motivate someone to keep reaching their daily recovery goal. This Qualtrics link will work on smartphones such that the SP can record and upload videos directly from their smartphone. If used on a computer, the SP will have to record the video using software such as Photo Booth on Mac or Windows Camera on PC, and then upload the video as a file to Qualtrics. SPs will also be asked to optionally provide information on the recovery work they do (e.g., facilitate a support group meeting on Wednesdays at 6pm) and how to access it (e.g., provide the zoom link or physical address of the recovery community center), and a brief demographic questionnaire. Finally, they will be asked under what circumstances the study team can contact them.

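### Section 7.2 tests whether video features differ by speaker demographics but names no adjustment for them when it correlates features with ratings

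*Combined protocol and SAP*

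**What the plan says.** Section 7.2 (Planned Analyses) sets out two steps for the coded video features, in this order.

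1. "Statistical analyses will also be used to determine whether video characteristics differ as a function of demographics of the people in the videos". Its example is a question about sex and speech: "are men more likely to have monotonous speech patterns than women".
2. Once the ratings are in, "correlational analyses will be performed to identify associations between content/audio/visual video variables and rating scores". Earlier in the same section the step is put more briefly: "Video ratings done by SRs will be correlated with features of the SP videos".

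No covariate, stratification, partial correlation or model is named for step 2. The only regression model in 7.2 is an example given for the drinking outcomes. Sections 7.2.1 (secondary objective analyses) and 7.2.2 (subject characteristics) are both marked not applicable. No analysis of ratings by SP demographics is planned.

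Section 3.3 makes it a secondary objective "to identify components of the videos recorded by SPs that were well-received by SRs". Section 4.2.2 gives the purpose: "to identify which characteristics are well-received by support-receivers, to guide future content creation". SP demographics are collected: section 4 says that each SP completes a short questionnaire, and section 6.1 lists it as "and a brief demographic questionnaire".

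**The concern.** Content advice is useful when it concerns something a speaker can change, such as looking at the camera, varying the voice or choosing a type of support message. It is less useful when it only restates who the speaker was. The plan itself raises the possibility that features go with speaker demographics, but it makes no stated use of that result when it turns to the ratings.

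Suppose SRs rate one group of speakers higher for some other reason. Every feature more frequent in that group then tends to correlate with the rating, even if it has no effect of its own. Because ratings are not to be compared across SP groups, the team would have no planned way to notice this. Future SPs could then be asked to copy a feature that does nothing.

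**Working it through.** The documents state no significance level, effect size or target correlation for this analysis, so there is no figure to reproduce. What follows is an illustration on assumed inputs.

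**From the documents:** up to 50 SPs and 30 SRs (section 5.2); 28 days of use (section 4.1).

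**Assumed:** one feature value and one mean rating per speaker; 50 speakers (the SP maximum) or 28 (a different speaker each night); one binary demographic with equal groups; no direct effect of the feature on the rating; a two-sided 5% test.

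**Formulas.** Let *a* be the correlation of the demographic with the feature and *b* its correlation with the rating.
- Spurious correlation: r = a × b.
- A group difference of *d* SD (within-group) corresponds to a = (d/2)/√(1 + d²/4). For d = 0.5, a = 0.25/√1.0625 = 0.24, so differences of 0.5 SD in both give r = 0.24 × 0.24 ≈ 0.06.
- In reverse, d = 2a/√(1 − a²). So a = 0.5 is 1.15 SD and b = 0.4 is 0.87 SD, giving r = 0.5 × 0.4 = 0.20.

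**False-positive rates**, simulated with 20,000 data sets per setting:

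| Group difference, feature / rating (SD) | a / b | Spurious r | Plain, n = 28 | Plain, n = 50 |
|---|---|---|---|---|
| 0.5 / 0.5 | 0.24 / 0.24 | 0.06 | 6.0% | 6.7% |
| 0.63 / 0.63 | 0.3 / 0.3 | 0.09 | 7% | 9% |
| 0.8 / 0.8 | 0.37 / 0.37 | 0.14 | 10.6% | 16.0% |
| 1.15 / 0.87 | 0.5 / 0.4 | 0.20 | 17–18% | 28–29% |
| 1.5 / 1.15 | 0.6 / 0.5 | 0.30 | 35–37% | 58–60% |

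Ranges within a cell come from separate simulations. The partial correlation given the demographic is positive about 5% of the time in every row.

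**The other direction.** Now let the feature truly correlate 0.4 with the rating, and let the demographic have no effect of its own on ratings.
- n = 28, a = 0.5: power falls from 58% (plain) to 45% (adjusted).
- n = 28, a = 0.6: 58% to 40%.
- n = 50, a = 0.6: 84% to 65%.

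**What the two values tell apart.** Take a = 0.5.
- Real effect only: the demographic–rating correlation is 0.5 × 0.4 = 0.20. The partial correlation is (0.40 − 0.5 × 0.20)/√((1 − 0.25)(1 − 0.04)) = 0.30/0.85 = 0.35, so 0.40 becomes 0.35.
- Speaker group only (b = 0.4): the numerator is 0.20 − 0.5 × 0.4 = 0, so 0.20 becomes 0.

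The pair of estimates is therefore more informative than either one alone.

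**The case against.** The strongest reply is that the aim is descriptive. The analysis is secondary and exploratory, it asks what is associated with good ratings, and a plain correlation answers that. SR comments on the videos may also inform what they like and dislike. This stands as a reason for low severity. It does not remove the gap, because the stated use is to steer content, which goes beyond description.

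Four stronger readings are tempting, and the documents do not support them.
- A reader might infer that the plan expects features to differ by demographics. It only tests whether they do, and its sex-and-speech example is a question.
- A reader might infer that the plan specifies unadjusted correlations. It is silent on adjustment. Plain correlation is the natural reading, but the wording does not rule out a partial correlation.
- A reader might infer that SRs do prefer some types of speaker. No section says so. Without that link there is no bias of this kind, and with modest differences it is trivial.
- A reader might infer that only the adjusted value should count. The power loss above shows that this is a trade-off: in a hypothesis-generating pilot, missing a real feature is also a cost.

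Two points about the design also stand. Section 6.1 shows a written transcript in place of the video on some nights, when SRs neither see nor hear the speaker, and section 4 says the demographic answers are not shared with SRs. Reactions to the type of speaker are then largely confined to video nights, which the simulation ignores. And the plan states no 5% decision rule for these correlations, so the false-positive rates measure the distortion and do not describe a planned decision.

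**Conclusion.** The concern holds in a limited form. The plan examines feature differences by SP demographics, names no adjustment for them in the feature–rating step, and intends to use the result to guide content. Any harm is conditional on both links existing: features must differ by speaker group, and ratings must differ by speaker group.

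On the assumptions above, the distortion is negligible when both differences are about 0.5 SD (6–7% against a nominal 5%). It is material when both are large (17–29% at correlations of 0.5 and 0.4). The documents do not show which case applies, and the analysis as written would not reveal it. Severity is minor: this is a secondary aim in a pilot, and a better method is available at almost no cost.

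**What to change.** In section 7.2, state that each feature–rating association will be reported twice: unadjusted, and as a partial correlation or regression adjusted for a small prespecified set of SP demographics. Gender is the obvious candidate, with age group if it is collected; the documents do not list the questionnaire items, so the set should be checked against the form. Where the two estimates diverge, describe the feature as possibly reflecting the type of speaker, and do not recommend it as content to copy. Judge divergence by the shift in the estimate. Loss of significance alone is not evidence of divergence, because adjustment also widens the interval.

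The cost is a sentence or two in 7.2, a few lines of analysis and two or three degrees of freedom. No new data are needed if the questionnaire holds these items. It should be treated as required, since the sentence in section 6.1 can be read as making it optional. With at most 50 SPs only a few covariates can be supported, and unmeasured speaker traits remain unadjusted. The downside is lower power for the adjusted estimate when a feature is closely tied to a demographic, which is why both values should be shown.

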7.2.1 Secondary Objective Analyses (if applicable)

N/A

7.2.2 Analysis of Subject Characteristics (if applicable)

N/A

7.2.3 Interim Analysis (if applicable)

We do not intend to have an interim analysis. Instead, we propose to monitor screening data, baseline demographics, retention data, serious adverse events data, and any other data that will help in the assessment of the study. Based on these data, we can determine if changes in recruitment or study termination are necessary.

7.3 Data Relevance

The quantitative and qualitative data collected in this study will provide the first pieces of evidence of LDART's feasibility, acceptability, and preliminary efficacy, which will determine how to improve upon the intervention.

7.4 Data Coding

QI: Two coders on the study team will develop code books independently, drawing from themes observed in the transcripts. The two coders will then merge their code books, resolving any discrepancies by mutual agreement and with input from other researchers.

For most qualitative (e.g., describe the background scene in the video) and quantitative analyses (e.g., how often does SP look directly at the camera?) of SP videos, we will have two coders on the study team rate these variables independently, and discrepancies will be resolved by mutual agreement and input from other members of the study team.

7.5 Data Analysis Tools

Statistical analyses will be performed using software such as MPlus, SPSS and Prism. Video quantification will be performed using software such as NVivo, Praat, and OpenFace. All QI analyses will be done in NVivo.

7.6 Data Monitoring

The Pls ([name] and [name]) are responsible for monitoring the data, ensuring protocol compliance, and conducting safety reviews. Data pertaining to recruitment, retention, follow-up rates, completeness, and availability of primary outcome data will be discussed at least monthly.

7.7 Handling of Missing Data

Intervention: In cases where significant amounts of missing data occur (>5%), multiple imputation in SPSS will be conducted. QIs: QIs will continue until there are data for each of the questions in the discussion guide. If no one interviewed has personal experience with a particular topic, that will be noted in the results.

8 Data/Specimen Handling and Record Keeping

8.1 Subject Data Confidentiality

Participant confidentiality and privacy are strictly held in confidence by the participating investigators, their staff, and the sponsor(s)/funding agency. Therefore, the study protocol, documentation, data, and all other information generated will be held in strict confidence. HIPAA guidelines for data collection, management and monitoring will be followed in this study. All personnel involved in this study have already been certified by the Yale Human Investigation Committee as having completed training in the protection of the rights of human subjects who participate in research. Therefore, the study protocol, documentation, data, and all other information generated will be held in strict confidence. All research activities will be conducted in as private a setting as possible (via Zoom, in a private physical space). Representatives of the Institutional Review Board (IRB), regulatory agencies or study sponsor/funding agency may inspect all documents and records required to be maintained by the investigator for the participants in this study. The study site will permit access to such records.

Video recordings of SPs will be stored and shared with SRs also via Qualtrics, a HIPAA-approved platform. Audio and video recordings of participants during QIs will be recorded using Zoom. The files will be saved on a secure USB hard drive and Yale Secure Box. Audio files will be transcribed and stored in de-identified form. Video files may be retained for nonverbal analyses, and deleted within 5 years after data collection is complete.

The study participant's contact information will be securely stored at each study site for internal use during the study (stored in Qualtrics and Yale Secure Box folder). At the end of the study, all records will continue to be kept in a secure location for as long a period as dictated by the reviewing IRB, institutional policies, regulatory, or sponsor/funding agency requirements. Study participant research data, which is for purposes of statistical analysis and scientific reporting, will be transmitted to and stored on study computers. This will not include the participant's contact or identifying information. Rather, individual participants and their research data will be identified by a unique study identification number. The study data entry and study management systems used will be secured and password protected. At the end of the study, all study databases will be de-identified and archived on Yale secure systems.

8.2 Data Quality Assurance

The entire study will be conducted by the same study PI ([name]) to ensure consistency. The study PI will consult with and be mentored by the other PI ([name]) who has extensive experience with conducting clinical trials and interventions for addiction. The QIs will be transcribed verbatim by a professional transcription service. Trained research staff will serve as secondary transcriptionists and will review all audio recordings and transcripts and make corrections as needed.

8.3 Data or Specimen Storage/Security

Data will be stored on password-protected, Yale-managed computers and secure online storage spaces e.g., Yale Secure Box and Qualtrics. Data will be de-identified with unique codes and a key in a document separate from the data. Specifically, confidentiality of sensitive or health-related information collected via surveys will be accomplished by assigning unique numeric identifiers to each subject, and exclusively using these numbers on all electronic data records which contain sensitive information. For example, demographic data in Qualtrics will be labeled using participants' unique numeric identifier (assigned to them at the time of enrollment) to keep their identifying information and their survey responses separate. Transcripts of QIs will not include names of participants but rather their numeric identifiers Apalysis of PHLE ALL UNIVERSITY OF PRICE OF PRICE OF ALL UNIVERSITY OF PRICE OF PRICE

8.4 Study Records

The study PI ([name]) will be responsible for maintaining all study documentation (protocols, consent forms, surveys, etc). These files will only be accessible to other members of the study team, via Secure Box.

8.5 Access to Source

Only members of the research team will have access to the data, recordings, and related transcripts.

8.6 Retention of Records

Records will be maintained for 5 years after study completion.

8.7 Data and Safety Monitoring Plan

The principal investigators (PIs) are responsible for monitoring the data, assuring protocol compliance, and conducting the safety reviews quarterly. During the review process, the PIs will evaluate whether the study should continue unchanged, require modification/amendment, or terminate enrollment. The PIs and the IRB have the authority to stop or suspend the study or require modifications.

This protocol presents minimal risks to the subjects. Unanticipated Problems Involving Risks to Subjects or Others (UPIRSOs), including adverse events, are not anticipated. In the unlikely event that such events occur, Reportable Events (which are events that are serious or life-threatening and unanticipated, or anticipated but occurring with a greater frequency than expected, and possible/probably/definitely related) or UPIRSOs that may require a temporary or permanent interruption of study activities will be reported immediately (if possible, followed by a written report within 5 calendar days of the PIs becoming aware of the event to the IRB and any appropriate funding and regulatory agencies. The PIs will apprise study personnel of all UPIRSOs and AEs that occur during the conduct of this research project via email as they are reviewed by the PIs. The protocol's research monitor(s), the Yale School of Medicine Office of Student Research, and regulatory and decision-making bodies will be informed of AEs such as a participant threatening harm to themselves or others within 5 days of the event becoming known to the PIs.

9 Study Considerations

